1.3 SCHEDULE OF ACTIVITIES AND SAMPLE COLLECTION SCHEDULE

Table 1 Schedule of Activities

Visit	SCR ^a	Double-Blind Treatment							UV ^c	Early D/C Visit ^d	Safety Follow-Up Visit ^e
	1	2	3	4	5	6	7	8			16 (or 4 weeks after Early D/C)
Study week		0	2 ^b	4	6 ^b	8	10 ^b	12			
Window in Days	-28 to -1	NA	±2	±2	±2	±2	±2	±2	NA	NA	±2
Informed consent ^f	x										
Review of eligibility criteria	x	x									
Randomization		x									
Demographic data	x										
Medical history and baseline conditions	x										
Review of contraception methods	x	x		x		x		x	x	x	x
C-SSRS	x			x		x		x	x	x	x
Vital signs ^g	x	x		x		x		x	x	x	x
Weight		x						x		x	x
Height		x									
Complete physical examination ^h	x	x						x	(x)	x	
Neurological examination ⁱ	x	x						x	(x)	x	
Query for potential unreported relapses		x		x		x		x	x	x	x
EDSS ^j	x	x						x	(x)	x	
12-lead ECG ^k	x	x		x				x		x	
Blood tests: ^l											
Hematology and full chemistry panel	x	x		x		x		x	(x)	x	x

Table 1 Schedule of Activities (cont.)

Visit	SCR ^a	Double-Blind Treatment							UV ^c	Early D/C Visit ^d	Safety Follow-Up Visit ^e
	1	2	3	4	5	6	7	8			16 (or 4 weeks after Early D/C)
Study week		0	2 ^b	4	6 ^b	8	10 ^b	12			
Window in Days	-28 to -1	NA	±2	±2	±2	±2	±2	±2	NA	NA	±2
Limited chemistry panel: ALT, AST, total and direct bilirubin testing			x		x		x				
Hepatic synthetic function testing (PT, INR, aPTT)	x							x	(x)		
Lipids		x						x		x	
Flow cytometry ^m	x	x ⁿ		x		x		x		x	x
Total Ig, IgG, IgA, IgM	x			x		x		x		x	x
Hepatitis B screening ^o	x										
Hepatitis B virus DNA	x			(x)				(x)		(x)	
Hepatitis C screening ^p	x										
HIV screening	x										
Tuberculosis Test (QuantiFERON®-TB Gold)	x										
Plasma PK sample ^q		x		x		x		x	(x)	x	
Additional intensive PK sampling (optional) ^q		x		x							
Serum and plasma biomarkers ^r	x	x ⁿ		x		x		x		x	x
RNA collection (PAXgene tube)	x	x ⁿ						x		x	x
In clinic pregnancy test ^s	x	x		x		x		x	(x)	x	x
Urinalysis		x		x				x	(x)	x	x

Table 1 Schedule of Activities (cont.)

	SCR ^a	Double-Blind Treatment									Safety Follow-Up Visit ^e
Visit	1	2	3	4	5	6	7	8			
Study week		0	2 ^b	4	6 ^b	8	10 ^b	12	UV ^c	Early D/C Visit ^d	16 (or 4 weeks after Early D/C)
Window in Days	-28 to -1	NA	±2	±2	±2	±2	±2	±2	NA	NA	±2
CSF collection (optional) ^t	x							x			
MRI ^u	x			x		x		x	(x)	(x)	
Concomitant medications	x	x		x		x		x	x	x	x
Adverse events	x	x		x		x		x	x	x	x
Study treatment dispensation		x		x		x		x ^v			
Study treatment compliance				x		x		x		x	

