RBR: RNA, serum and plasma samples (optional) ^w	x	x ⁿ		x		x		x		x	x
RBR: DNA (optional) ^w		x ^x									

C-SSRS= Columbia-Suicide Severity Rating Scale; CSF= cerebrospinal fluid; DBT= double-blind treatment; D/C= discontinuation; eCRF = electronic Case Report Form; EDSS= Expanded Disability Status Scale; HBcAb= hepatitis B core antibody; HBsAg= hepatitis B surface antigen; Ig= immunoglobulin; MRI= magnetic resonance imaging; OLE= open-label extension; PK= pharmacokinetic; RBR= research biosample repository; SCR.= screening; TB= tuberculosis; ULN= upper limit of normal; UV= unscheduled visit; x required, (x) not always required.

Table 1 Schedule of Activities (cont.)

- ^a Participants are permitted one re-screening. As a general guideline, MRI scan, EDSS, RBR, hematology, chemistry, urinalysis, CD4, ECG, immunoglobulins, hepatitis B, C, HIV, hepatic synthetic function testing, lipids, flow cytometry, and TB screening and biomarkers samples should be repeated if there is more than 6 weeks between the screening *assessment date* and re-screening *assessment date*. All other procedures listed in the schedule of activities for the screening visit should be repeated at the re-screening visit. Any screening assessment may be repeated at a re-screening visit if judged by the investigator to be clinically necessary.
- ^b *It is preferred that the blood tests performed at these visits are analyzed by the central laboratory during a clinic visit. However, if these are performed by an accredited local laboratory, the results and reference ranges must be added to the appropriate adverse event eCRF form when applicable.*
- ^c UV may be performed, as clinically appropriate. It must be performed in the following situations: 1) if the patient is experiencing neurological worsening, 2) if the patient has $> 3 \times$ ULN AST or ALT, or 3) if the patient is experiencing symptoms that could be associated with worsening liver function. Assessments at UVs may be performed as clinically indicated. In the case of abnormalities in transaminase levels or clinical indications of worsening liver function, additional laboratory testing may be required per medical monitor guidelines (see Table A6-1).

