- ^d Participants who discontinue from the study prior to completion should be encouraged to return to the clinic for an Early D/C visit. If a patient states intention to discontinue participation at the Week 4, Week 8, or an UV prior to Week 12, that visit should be converted to an Early D/C Visit.
- ^e A Safety Follow-up Visit should be performed in 2 situations: 1) 4 weeks after early discontinuation of study drug, or 2) for participants that complete the double-blind treatment period (Week 12) who do not elect to participate in the OLE, in which the visit should be performed at Week 16.
- ^f Informed consent must be documented before any study-specific screening procedure is performed.
- ^g Includes respiratory rate, pulse rate, and systolic and diastolic blood pressure while the participant is in a seated position, and temperature. Temperature should be noted in the participant's notes only.
- ^h Includes an evaluation of the head, eyes, ears, nose, and throat and evaluation of the cardiovascular, dermatologic, musculoskeletal, respiratory, gastrointestinal, and neurological systems; genitourinary examinations may be performed if clinically indicated.
- ⁱ A separate neurological examination should be performed by the treating physician if the treating physician is not performing the EDSS. During an UV, the neurological examination must be performed if the participant is experiencing neurological worsening between scheduled visits.
- ^j The EDSS can be performed by either the treating investigator or a separate examining investigator. The person performing the EDSS must have a valid Level C Neurostatus certification.
- ^k ECG recordings must be performed after the participant has been resting in a supine position for at least 10 minutes.
- ^l Participants should fast prior to the blood draws for Visits 2, 3, 4, and 5.
- ^m Flow cytometry: Analysis may include, but is not limited to, the determination of B-cell and T-cell numbers and other lymphocyte subsets.
- ⁿ *Biomarker and RBR samples should be collected prior to the administration of study drug (predose).*

Table 1 Schedule of Activities (cont.)

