7. DISCONTINUATION OF STUDY TREATMENT AND PARTICIPANT DISCONTINUATION OR WITHDRAWAL

7.1 DISCONTINUATION OF STUDY TREATMENT

It may be necessary for a participant to permanently discontinue (definitive discontinuation) study treatment. If study treatment is definitively discontinued, the participant should move to the Safety Follow-up Period. Refer to the schedule of activities (see Section 1.3) for data to be collected at the time of discontinuation of study treatment (“Early Discontinuation Visit”) and the further follow-up evaluations that need to be completed in the Safety Follow-up Period.

Participants must permanently discontinue study treatment if they experience any of the following:

- Any medical condition that the investigator or Sponsor determines may jeopardize the participant's safety if he or she continues to receive study treatment
- Investigator or Sponsor determination that treatment discontinuation is in the best interest of the participant
- Demonstrate active hepatitis B infection
- PML
- First observation of AST or ALT elevation $> 8 \times$ ULN
- AST or ALT elevation $> 5 \times$ ULN persisting more than 2 weeks
- AST or ALT elevation $> 3 \times$ ULN in combination with any of the following:
 - Total bilirubin $> 2 \times$ ULN or clinical jaundice as defined by Hy’s Law
 - INR > 1.5
 - Symptoms of hepatitis, such as fatigue, nausea, vomiting, right upper quadrant pain or tenderness
 - Signs or symptoms of immune-related hepatotoxicity (fever, rash, or eosinophilia $> 5\%$)
- *ALT or AST elevation between $3\text{--}5 \times$ ULN (inclusive) persisting for 4 weeks and in absence of alternative etiology*
- Grade 3 neutropenia (ANC $500\text{--}1000/\text{mm}^3$) persisting more than 1 month or reoccurring
- Grade 4 neutropenia (ANC $< 500/\text{mm}^3$)
- Grade 2 thrombocytopenia (platelet count $50,000\text{--}75,000/\text{mm}^3$) persisting more than one month or reoccurring
- Grade 3 thrombocytopenia (platelet count $25,000\text{--}50,000/\text{mm}^3$) or Grade 4 thrombocytopenia ($< 25,000/\text{mm}^3$)
- Malignancy (with the exception of non-serious local and resectable basal or squamous cell carcinoma of the skin)

- Pregnancy

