Appendix 6: Safety Plan: Management of Identified and Potential Risks

Table A6-1 Guidelines for Management of Participants Who Experience Adverse Events (cont.)

Event	Action to Be Taken
Liver function test elevation	
AST or ALT > 3.0–5.0 × ULN	
 • Repeat testing of ALT, AST, ALP, total and direct bilirubin, GGT, CPK, LDH, complete blood count with differential, coagulation tests, and the “LFT unscheduled” lab kit within 48–72 hours; inquire about symptoms, co-medications, co-morbidities, and alternative causes (refer to Appendix 7). The medical monitor will provide guidance on additional lab testing that may be required. • If ALT or AST > 3 × ULN is confirmed on repeat testing, continue close observation (repeat testing of ALT, AST, ALP, and total bilirubin) every 48–72 hours until transaminases stabilize, then weekly until AST and ALT < 3 × ULN. Maintain study drug dosing. • If study drug was stopped, re-challenge is allowed. • Permanently discontinue study drug if AST or ALT > 3.0 × ULN persists for 4 weeks in absence of alternative etiology or if close observation is not possible. • Record as an adverse event.
AST or ALT > 5.0–8.0 × ULN	
 • Repeat testing of ALT, AST, ALP, total and direct bilirubin, GGT, CPK, LDH, complete blood count with differential, coagulation tests, and the “LFT unscheduled” lab kit within 48–72 hours; inquire about symptoms, co-medications, co-morbidities, and alternative causes (refer to Appendix 7). The medical monitor will provide guidance on additional lab testing that may be required. • Continue close observation (repeat testing of ALT, AST, ALP, and total bilirubin) every 48–72 hours until transaminases stabilize, then weekly until AST and ALT < 3 × ULN. • Discontinue study drug if AST or ALT > 5 × ULN persist more than 2 weeks or if close observation is not possible. • Re-challenge is not permitted. • Report as an adverse event of special interest within 24 hours.

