### **5.4.2 Supportive Secondary Endpoint(s)**

The secondary safety endpoints are:

- Incidence and severity of adverse events
- Change from baseline in vital signs
- Change from baseline in targeted clinical laboratory test results (Hematology, chemistry, hepatic synthetic function tests, lipids, and Igs)
- Proportion of participants with suicidal ideation or behavior, as assessed by Columbia-Suicide Severity Rating Scale

The secondary PK endpoint is:

- Plasma concentration of fenebrutinib at specified timepoints

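### PT/INR/aPTT is the only SAP-targeted laboratory family with no draw at the Early D/C visit, so participants who stop before Week 12 have no scheduled post-baseline coagulation value

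*Protocol*

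**What the plan says.** SAP Section 5.4.2 defines the laboratory secondary safety endpoint as "Change from baseline in targeted clinical laboratory test results (Hematology, chemistry, hepatic synthetic function tests, lipids, and Igs"). SAP Section 5.4.2.1 plans to display laboratory results over time, and adds a shift table of selected tests from baseline to the worst post-baseline grade. It does not say whether values from unscheduled visits enter either display.

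The draws are set in protocol Section 1.3, Table 1. The row "Hepatic synthetic function testing (PT, INR, aPTT") has a required mark at screening and at Week 12, a conditional mark at unscheduled visits, and nothing at Early D/C or Safety Follow-Up. The table legend reads "x required, (x) not always required". By contrast, the row "Total Ig, IgG, IgA, IgM" is marked at Early D/C, as are the hematology and full chemistry row and the lipids row.

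Three further provisions matter:

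- Protocol Section 7.1: "If study treatment is definitively discontinued, the participant should move to the Safety Follow-up Period".
- Table 1, footnote d: if a participant announces at Week 4, Week 8 or an unscheduled visit before Week 12 that they intend to stop, "that visit should be converted to an Early D/C Visit".
- Table 1, footnote c, on unscheduled visits: "It must be performed in the following situations". The situations listed are neurological worsening, AST or ALT above 3 x ULN, and symptoms that could reflect worsening liver function. For AST or ALT above 3 x ULN, Table A6-1 in Appendix 6 asks for repeat testing within 48 to 72 hours, including "complete blood count with differential, coagulation tests".

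**The concern.** The SAP treats the five families alike, but the schedule does not collect them alike. For a participant who leaves before Week 12, four families have a closing value and the coagulation family has none by schedule. Any value that does exist arose because something prompted a test. A change-from-baseline summary for PT, INR and aPTT would then rest on Week 12 attenders, plus perhaps a few triggered results that the SAP does not say how to use.

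The parameter is of interest for this drug. Appendix 6 lists transaminase elevation as a risk of fenebrutinib, and more severe liver injury and bleeding as potential risks. INR above 1.5 forms part of a discontinuation criterion (Section 7.1) and of a definition of adverse events of special interest (Section 8.3.8), in each case together with raised AST or ALT. No reason is given for leaving this family out of a visit at which blood is already taken.

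**Working it through.** **Step 1. Compare the SAP list with Table 1, row by row (double-blind phase).**

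| Family in SAP 5.4.2 | Pre-treatment | Scheduled post-baseline | Unscheduled visit | Early D/C | Safety Follow-Up |
|---|---|---|---|---|---|
| Hematology | Screening, Week 0 | Weeks 4, 8, 12 | conditional | yes | yes |
| Chemistry (full panel) | Screening, Week 0 | Weeks 4, 8, 12 | conditional | yes | yes |
| Lipids | Week 0 | Week 12 | none | yes | no |
| Immunoglobulins | Screening | Weeks 4, 8, 12 | none | yes | yes |
| PT/INR/aPTT | Screening | Week 12 | conditional | **no** | no |

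Four of five families have an Early D/C draw; PT/INR/aPTT is the exception. Lipids are also absent at Safety Follow-Up, so Early D/C is the column in which coagulation stands alone.

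**Step 2. Follow a participant who stops before Week 12.** Section 7.1 moves that person to safety follow-up, so the Week 12 draw is not reached. Neither the Early D/C column nor the Safety Follow-Up column has a coagulation mark. Scheduled post-baseline coagulation values: zero. Footnote d can also turn an unscheduled visit, whose column has a conditional coagulation mark, into an Early D/C visit, whose column has none.

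**Step 3. Identify what is still captured.** Every Table A6-1 row with AST or ALT above 3 x ULN asks for coagulation tests, including the rows with permanent discontinuation. Early stoppers with a liver trigger should therefore have values. The bleeding rows of Table A6-1 name no coagulation test, and stops for other reasons prompt none.

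**Step 4. Size it.** Inputs: N = 102, with 68 on fenebrutinib and 34 on placebo, and 3% dropout (protocol Section 9.2; SAP Section 3). Participants without the scheduled value = dropout x N.

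- Planned 3%: 0.03 x 102 = 3.06 (0.03 x 68 = 2.04 fenebrutinib; 0.03 x 34 = 1.02 placebo). About 99 keep a Week 12 value.
- Assumed 5%: 0.05 x 102 = 5.1.
- Assumed 10%: 0.10 x 102 = 10.2.
- Assumed 15%: 0.15 x 102 = 15.3.

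The last three rates are assumptions; the plan gives only 3%.

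**Step 5. Size the triggered testing.** Appendix 6, Section A6-1.1, reports Grade 2 or higher transaminase elevation in 1% to 10% of participants on fenebrutinib 200 mg BID. If that range applied here, 0.01 x 68 = 0.68 to 0.10 x 68 = 6.8 fenebrutinib participants would have triggered coagulation tests, whether or not they stop early.

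**The case against.** The strongest reply is that the participants who matter most for this laboratory family are already covered. Raised transaminases make an unscheduled visit mandatory, the coagulation row allows a draw there, and Table A6-1 asks for coagulation tests in every relevant row. Symptoms suggesting worsening liver function also force a visit. Early stoppers still give full chemistry at Early D/C, including transaminases, bilirubin and albumin. The summaries are descriptive, and the shift table is not worded as limited to scheduled visits.

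Most of that stands, and it rules out three stronger readings that a reader might infer from the blank cell:

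- *That coagulation is measured only in Week 12 completers.* The conditional mark and Table A6-1 contradict this.
- *That the missing values favour fenebrutinib.* Hepatic leavers are the ones with triggered tests, so the observed values may be enriched for abnormality. Nothing in the documents shows that the untested leavers are more likely to be abnormal.
- *That the whole secondary endpoint is lost for early stoppers.* It is one family of five.

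An extreme case does not rescue the stronger readings. Suppose all 3 dropouts were on fenebrutinib, all had INR above 1.5, and none had a liver trigger. A report of 0/65 (95% CI 0 to 5.5%) would then replace 3/68 = 4.4% (0.9 to 12.4%). The 4.4% already lies inside the reported interval.

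The reply does not close the gap for early stoppers without a liver trigger. The unscheduled draw is conditional, and Section A6-2.3 describes the Table A6-1 rules as guidance. The SAP's silence on unscheduled values leaves even the triggered results without a stated use.

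**Conclusion.** The point holds as a mismatch between the SAP's list of targeted laboratory families and the Table 1 schedule. Participants who stop before Week 12 have no scheduled post-baseline PT/INR/aPTT. Those with AST or ALT above 3 x ULN should have triggered results; those without a liver trigger may have none. What is available for early stoppers is therefore selectively observed, in a direction that the documents do not establish.

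The size is about 3 of 102 participants (about 2 fenebrutinib, 1 placebo). This assumes that the planned 3% dropout approximates the share missing the Week 12 draw and that dropout is proportional to arm size. It is an upper figure, since some of those participants may have triggered values. The INR-based stopping and reporting rules are not undermined, because they apply together with raised AST or ALT, which itself calls for coagulation tests. This is a cheap improvement to data collection; it does not threaten the trial's conclusions.

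**What to change.** 1. In protocol Table 1, add a required mark in the Early D/C cell of the hepatic synthetic function row, so that all five SAP families are drawn there.
2. In SAP Section 5.4.2.1, state that Early D/C and unscheduled PT/INR/aPTT values enter the change-from-baseline and worst post-baseline shift summaries. Class each as on- or off-treatment from the actual date of last dose. It should not be assumed to be on-treatment: the Early D/C visit has no window in Table 1, and participants who leave are only encouraged to attend.
3. The matching Early D/C cell in Table 2 is also blank, but changing it is optional because the open-label extension lies outside the controlled comparison.

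The cost is one table cell, a short addition to the SAP, and one extra coagulation tube at a visit where blood is already drawn. The draw will not recover every early stopper, since some will not attend.

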- ° Tests required for hepatitis B screening: HBsAg, total HBcAb, and viral DNA PCR. Participants with a positive HBsAg must be excluded. Participants with a positive HBcAb are permitted provided viral DNA PCR is negative. Participants with a positive HBcAb but negative HBV DNA PCR will have their hepatitis B viral DNA monitored as per the schedule of activities.
- ° Hepatitis C screening: HCAb must be negative.
- ° Please refer to [Table 3](#) for more details.
- ° Biomarker samples should be collected ± 3.5 days from MRI scan. Note: Not all biomarker samples will be collected at each MRI visit; however, those that are collected should be collected as close to the MRI scan as possible.
- ° All women of childbearing potential will have a serum pregnancy test at screening. Urine pregnancy tests will be performed at specific subsequent visits. If a urine pregnancy test is positive, it must be confirmed by a serum pregnancy test.
- ° The Day 1 CSF collection by lumbar puncture should only be performed once other screening tests confirm that the patient qualifies for the study. Lumbar puncture can be performed anytime during the screening period or at Day 1 prior to dosing. The Week 12 lumbar puncture should to be performed between 1 to 2 hours after the administration of study drug in clinic. A contemporaneous plasma PK sample should be collected at the time of CSF collection to enable comparison of CSF and serum drug levels. *If the Week 12 lumbar puncture is missed, it can be performed at a later visit, including an OLE visit.*
- ° MRI scans should be obtained as close to the scheduled visit as possible (± 3 days) and may be obtained at UV if medically warranted. MRI scan may not be performed earlier than 3 weeks after IV corticosteroid treatment for MS relapses. At the study D/C visit, an MRI scan should be obtained if an MRI scan was not performed during the prior 4 weeks.
- ° Study treatment will only be dispensed for participants continuing in the optional OLE.
- ° RBR: Not applicable at a site that has not been granted approval for RBR sampling. Performed only for patients at participating sites who have provided written informed consent to participate.
- ° A single, DNA sample will be collected for RBR at the baseline visit. If the DNA sample is not taken at Visit 2 (baseline), the sample may be taken at any subsequent timepoint during the trial.

Table 2 Schedule of Activities: Open-Label Extension Phase

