8.1 EFFICACY ASSESSMENTS

8.1.1 Magnetic Resonance Imaging

Magnetic resonance imaging (MRI) is a useful tool for monitoring CNS lesions in MS. Different MRI derived parameters have been related to clinical activity and T1 weighted Gd-enhancing lesions or new and/or enlarging hyperintense T2 lesions have been related to relapses.

Radiologic evaluation for the primary efficacy parameter will be performed using a standardized MRI protocol at screening, and at Weeks 4, 8, and 12. Measurements from the screening MRI scan sequences will be used for the baseline MRI measurements; therefore, these sequences do not need to be repeated at the baseline visit. In addition, mandatory MRI scans will be obtained in participants who withdraw from study treatment (at withdrawal visit) if one was not performed during the prior 4 weeks. *While MRI scans are acquired in this study to support the primary and secondary endpoints, the set of images from each examination allows for the possibility of additional exploratory measurements.*

All MRI scans will be read by a centralized reading center for efficacy endpoints. The centralized reading center will be blinded to treatment assignment, and the reading will be performed in the absence of clinical information. Further details on scanning acquisition sequences, methods, handling, and transmission of the scans, certification of

site MRI radiologist/technicians, and the procedures for the blinded analysis of the scans at the central reading center will be described in separate MRI acquisition procedures manuals *and Imaging Review Charters*.

All MRI scans will also be reviewed locally by a radiologist for safety, and a MRI scan report containing only non-MS pathology will be provided to the treating investigator. During the DBT phase, only the local radiologist/technician at the investigational site who is assigned to this study may have access to the MRI scans, except at screening when the treating investigator may view the MRI scan. To maintain the blind, the treating investigator must not review the MRI scans obtained after randomization unless a safety concern arises. In the event that the treating investigator becomes aware of these MRI results, this should be documented in the eCRF, indicating the reason. The treating investigator may have access to MRI scans performed during the OLE phase *from their MRI facility*.

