#### **5.3.1 Definition of Primary Endpoint(s)**

The primary endpoint will be tested using a two-sided significance level of 0.05.

Radiologic evaluation for the primary efficacy parameter will be performed using a standardized MRI protocol at screening, and at Weeks 4, 8, and 12. All MRI scans will be read by a centralized reading center for efficacy endpoints. The centralized reading center will be blinded to treatment assignment, and the reading will be performed in the absence of clinical information. All MRI scans will also be reviewed locally by a radiologist for safety, and a MRI scan report containing only non-MS pathology will be provided to the treating investigator.

The total number of new gadolinium-enhancing T1 lesions will be calculated as the sum of the individual number of new lesions observed at Weeks 4, 8 and 12.

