#### **5.3.2 Main Analytical Approach for Primary Endpoint(s)**

The primary estimand follows a hypothetical strategy and estimates the treatment effect of fenebrutinib versus placebo had the patient not experienced a protocol defined intercurrent event on the basis of the following attributes:

- Population: all randomized participants.
- Variable: total number of new T1 Gd+ lesions as described in Section [5.3.1](#)
- Treatment:
  - 200 mg BID oral fenebrutinib
  - placebo
- Intercurrent events:
  - Withdrawal from treatment: Data after participants withdrawn from treatment will be censored, following a hypothetical strategy.
  - Initiation of another MS therapy: Initiation of another MS therapy is not allowed while on study. In case of such intercurrent event, patient will be considered as censored after initiation of another MS therapy, following a hypothetical strategy.
- Population-level-summary estimator: The total number of new T1 Gd+ lesions of primary analysis will be compared between the fenebrutinib and placebo using the negative binomial model, adjusting for stratification factor(s) (presence or absence of T1 Gd+ lesions on the screening MRI). In case of early discontinuations, different number of scans among participants may be observed. Log-transformed number of

scans will be included in the negative binomial model as an “offset” variable to account for different number of scans. The rate ratio and its two-sided 95% confidence intervals will be presented along with the p-value.

- Handling of missing data:
  - Withdrawal from study: no imputation will be conducted for missing data. The negative binomial model with number of scans as an “offset” variable accounts for different number of scans.

If the model fails to converge due to high number of zero T1 Gd+ lesion counts, a logistic regression model will be performed on the status of new T1 Gd+ lesion post-baseline (present or not) adjusted for the same stratification factor(s). The odds ratio and its two-sided 95% confidence intervals will be presented along with the p-value. A hypothetical strategy will be used as defined above.

Number of new T1 Gd+ lesions and proportion of participants with new T1 Gd+ lesions at each scheduled visit will be summarized by treatment groups.

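### A Week 8 visit converted to an Early D/C Visit may omit its scheduled primary-endpoint MRI, depending on a few days of scheduling (minor)

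*Protocol*

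**What the plan says.** **Schedule.** Protocol Table 1 marks MRI as required at Weeks 4, 8 and 12 and puts it in brackets in the Early D/C column. The key reads "x required, (x) not always required". The safety follow-up column has no MRI.

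**Conversion.** Under footnote d of Table 1, if a participant states at Week 4, at Week 8 or at an unscheduled visit before Week 12 that they intend to stop participating, "that visit should be converted to an Early D/C Visit".

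**The four-week condition.** The MRI footnote of Table 1 says "At the study D/C visit, an MRI scan should be obtained if an MRI scan was not performed during the prior 4 weeks". Protocol Section 8.1.1 says "mandatory MRI scans will be obtained in participants who withdraw from study treatment (at withdrawal visit", under the same condition. On timing, the footnote says "MRI scans should be obtained as close to the scheduled visit as possible (± 3 days" either way.

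**Analysis.** SAP Section 5.3.1 defines the primary endpoint as the "sum of the individual number of new lesions observed at Weeks 4, 8 and 12". SAP Section 5.3.2 says of treatment withdrawal: "Data after participants withdrawn from treatment will be censored, following a hypothetical strategy". It expects that "different number of scans among participants may be observed" and handles this with the log number of scans as an offset, without imputation.

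**The concern.** A scan due at Week 8 is part of the primary endpoint. If the participant is still taking study drug at that visit, it is an ordinary on-treatment observation, which the hypothetical estimand should use. Conversion moves it from required to conditional. The condition (no scan in the prior four weeks) is met or missed according to whether the Week 4 scan ran a day or two late or the Week 8 visit a day or two early. Safety follow-up has no MRI, so a scan omitted here is not recovered.

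The missing scan belongs to someone who is leaving, possibly because of disease activity or toxicity. The protocol itself treats some departures as informative: in Sections 9.4.2 and 9.4.3 the binary analyses count participants who withdraw for lack of efficacy or death, with no lesions seen, as having lesions. The offset corrects the negative binomial model for the number of scans, but not for a scan that is missing because of the lesions it would have shown. The lesion-free secondary endpoint uses logistic regression, for which no scan offset is planned.

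**Working it through.** **1. The plan's own sample size.** Protocol Section 9.2 and SAP Section 3 give 102 participants (68 and 34), at least 90% power, a 60% reduction, 0.7 new lesions per placebo scan and 3% dropout. SAP Section 2 gives two-sided alpha 0.05. Over three scans the means are 3 × 0.7 = 2.1 on placebo and 2.1 × 0.40 = 0.84 on fenebrutinib. The dispersion k is not given, so it is an assumption here. With the usual Wald formula and k = 1.0:

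placebo n = (1.960 + 1.282)² × [(1/2.1 + 1) + (1/0.84 + 1)/2] / (ln 0.40)² = 32.2, rounded up to 33.

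With 66 on fenebrutinib that makes 99. Then 99/0.97 = 102.1 (103 when rounded up) and 99 × 1.03 = 102.0. So 102 is consistent with k of about 1.0, but cannot be reproduced uniquely.

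**2. When the Week 8 scan is waived.** Protocol Table 3 puts Week 4 at Day 29 and Week 8 at Day 57. The MRI window is ±3 days, so the Week 4 scan falls on Days 26 to 32. The visit window is ±2 days, so the Week 8 visit falls on Days 55 to 59. The gap is visit day minus scan day. Its minimum is 55 − 32 = 23 and its maximum is 59 − 26 = 33. There are 7 × 5 = 35 pairs:

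| Gap | Day pairs | Scan at a converted Week 8 visit |
|---|---|---|
| Under 28 days | 5 + 4 + 3 + 2 + 1 = 15 | not called for |
| Exactly 28 days | 5 | wording does not settle it |
| Over 28 days | 15 | called for |

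These are counts of possible pairs, not probabilities. A converted Week 4 visit is hardly affected, because the preceding scan is the screening scan and usually lies more than four weeks back.

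**3. Scans at stake.** Leavers: 102 × 0.03 = 3.06. Scheduled scans: 102 × 3 = 306. If every leaver left at a converted Week 8 visit and lost that scan, the loss would be 3.06/306 = 1.0%.

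**4. Power.** A participant with s scans at per-scan rate r contributes information rs/(1 + krs) on the log rate. Summing gives I₀ (placebo) and I₁ (fenebrutinib), with SE² = 1/I₀ + 1/I₁ and power = Φ(|ln 0.40|/SE − 1.960). All leavers are assumed to leave at Week 8, with one scan if the Week 8 scan is waived and two if it is kept. Example with k = 1.0 and 3% dropout:

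- Waived: I₀ = 32.98 × 0.677 + 1.02 × 0.412 = 22.76; I₁ = 65.96 × 0.457 + 2.04 × 0.219 = 30.56; SE = 0.2769; power 91.14%.
- Kept: I₀ = 32.98 × 0.677 + 1.02 × 0.583 = 22.94; I₁ = 65.96 × 0.457 + 2.04 × 0.359 = 30.84; SE = 0.2757; power 91.36%.

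| k (assumed) | 3% dropout: waived → kept | 10% dropout (assumed): waived → kept |
|---|---|---|
| 0.5 | 97.54% → 97.65% | 97.07% → 97.46% |
| 1.0 | 91.14% → 91.36% | 90.26% → 91.04% |
| 1.5 | 83.01% → 83.29% | 81.99% → 82.93% |
| 2.0 | 75.00% → 75.28% | 73.99% → 74.94% |

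The largest difference at 3% dropout is about 0.3 percentage points.

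**The case against.** The best defence is that nothing forbids the scan. The bracketed mark means not always required, and many sites would do the MRI because it is due. With a ±3-day window the Week 8 scan may already have been done before the visit, and then nothing is lost. The planned dropout is low, and the offset removes a missing scan from the denominator as well as the count. All of this stands and keeps the point small. It does not change the fact that the text leaves a primary-endpoint scan to a coincidence of dates.

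A reader might infer more than the documents support:

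- *That the SAP discards the withdrawal scan.* It censors data after withdrawal from treatment. Someone who announces the intention at Week 8 may still be on drug when scanned, and the SAP is silent on that scan. A scan clearly after the last dose is off-treatment data, and excluding it agrees with the stated hypothetical strategy.
- *That the waiver and the censoring rule compound.* They cannot meet at one visit. If a scan was done in the prior four weeks, no withdrawal scan is called for; if none was, it is obtained.
- *That stopping treatment generally costs data.* After a stop on a Week 6 or Week 10 liver test, the last scheduled scan is about two weeks old, so no withdrawal scan is usually mandated. Scans before withdrawal are kept.
- *That most converted Week 8 visits lose their scan.* This needs the five ties counted as waived and all day pairs equally likely. The text supports neither.
- *That one leaver could noticeably distort the placebo count.* At the planned rate, a waived placebo scan carries 0.7 of an expected 34 × 3 × 0.7 = 71.4 lesions, about 1%, and the offset adjusts for the missing scan.

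**Conclusion.** The point holds in a narrow form and is minor. Footnote d, the bracketed MRI entry and the four-week condition together allow a converted Week 8 visit to omit its scheduled MRI. At the planned 3% dropout the cost is at most about 1% of scans and about 0.3 percentage points of power. That bound assumes every leaver leaves at Week 8 and loses the scan, and it rests on a dispersion range that the documents do not give. What remains is avoidable loss that may be informative, and it would matter more if dropout exceeded 3% or differed by arm.

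Separately, the SAP gives no censoring date and does not say how an Early D/C scan maps to Week 4, 8 or 12. That is missing detail, not a contradiction.

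**What to change.** In Protocol Table 1 (footnote d and the MRI footnote) and Section 8.1.1, state that when a Week 4 or Week 8 visit is converted to an Early D/C Visit, the MRI scheduled for that visit is still obtained. Add that, if taken on treatment, it counts as that week's scan in both the lesion sum and the offset.

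As a secondary clarification before unblinding, SAP Sections 5.3.1 and 5.3.2 should define the censoring date and how any other Early D/C scan is assigned to Week 4, 8 or 12.

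The cost is a few sentences. The downside is one scan, already scheduled, in a participant who is leaving.
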